8.3.2 Follow-up of AEs and SAEs

Any AEs that are unresolved at the participant's last assessment in the study are followed up by the investigator for as long as medically indicated, but without further recording in the eCRF. AstraZeneca retains the right to request additional information for any participant with ongoing AE(s)/SAE(s) at the end of the study, if judged necessary.

After the initial AE/SAE report, the Investigator is required to proactively follow each participant at subsequent visits/contacts. All SAEs and non-serious AEs will be followed until resolution, stabilisation, the event is otherwise explained, or the participant is lost to follow-up.

Adverse event variables

The following variables will be collected for each AE:

- AE (verbatim)
 - The capture of diagnoses is preferred over all associated signs and symptoms. For example: laboratory TLS, clinical TLS, cytokine release syndrome. Provisional diagnoses (eg, PHL) must be updated as soon as possible.
- The date when the AE started and stopped
 - When the onset of an AE in relation to dosing is rapid, for example TLS, it is important to record the **exact time of the start of infusion** dosing and the **time of AE onset** in addition to the dates.
- CTCAE grade/changes in CTCAE grade
- **For TLS events:** Adverse events of TLS shall be graded according to CTCAE. The AE verbatim shall discriminate between laboratory and clinical TLS. In addition, TLS events will be graded according to Howard modification of the Cairo-Bishop grading system (see [Appendix G](#)) on the TLS monitoring eCRF form.
- Whether the AE is serious or not

- Investigator causality rating against the IP(s) (yes or no)
- Action taken with IP(s) in response to the AE (for example: no action, dose reduced, treatment temporarily stopped, treatment permanently discontinued).
- Outcome of the event

In addition, the following variables will be collected for SAEs:

- Date AE met criteria for SAE
 - The date of start of first signs and symptoms should be captured together with the date the event became serious.
- Date investigator became aware of SAE
- Reason AE is classified as serious
- Date of hospitalisation
- Date of discharge
- Probable cause of death
- Date of death
- Autopsy performed (yes/no)
- Causality assessment in relation to Study procedure(s)
- Causality assessment to other medication

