10.4.4 Safety Review Committee

A study-specific SRC will provide ongoing safety surveillance of the study, with regularly scheduled reviews of safety, PK, and other relevant data.

The SRC will be responsible for making recommendations for dose confirmation or modification. All participants will be followed for safety through the entire duration of treatment.

A comprehensive initial review of all safety data will be conducted in approximately the first 6 participants of each cohort (safety run-in), with separate SRCs for each cohort executed independently. Recruitment will not be paused during this review. These participants will be

followed until all have completed Cycle 1, to ensure the treatment schedule is safe and tolerable. The SRC will review the totality of all relevant data (eg clinical, laboratory, safety) prior to providing decisions on study conduct. All decisions by this committee will be documented and shared in writing with all participating sites.

If, on an ongoing basis, > 25% of participants experience any AEs related to study intervention that result in discontinuation of study treatment, study data will be evaluated by the SRC. Enrolment may be paused until the safety data review by the SRC has been completed. Following this SRC review, additional monitoring may be implemented and/or enrolment and dosing may resume at a lower dose level or on a modified schedule. The SRC will meet at least every 6 months to review the overall safety and clinical data from the study.

At any time point during the study, the occurrence of a fatal AE deemed related to study therapy (after full etiological work-up and in discussion with the SRC) will result in study drug interruption and a comprehensive review of safety.

10.5 Study Population – Module 1

Refer to Section 5.1 and Section 5.2 in core protocol for inclusion and exclusion criteria, respectively.

10.6 Study Intervention – Module 1

AZD4573 is administered as an absolute (flat) dose, 2-hour (\pm 15 minutes) intravenous infusion on a once weekly schedule. CCI

Arm name	N/A
Intervention name	AZD4573
Type	Drug
Dose formulation	Concentrate for solution for infusion
Unit dose strength(s)	1.5 mg/ml
Dosage level(s)	6 mg AZD4573 (starting dose) 9 mg AZD4573 12 mg AZD4573 (target dose)
Route of administration	IV infusion
Use	Experimental
IP or NIP	IP
Sourcing	Provided centrally by the sponsor

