10.6.1 Dose Modification

Dose modification and discontinuation guidelines for haematological and non-haematological toxicities (excluding abnormal liver chemistry test results) are shown below in [Table 11](#). Dose modifications for AZD4573 for abnormal liver chemistry test results are described in [Table 12](#).

In general, if a participant experiences a Grade 1 or Grade 2 haematological or non-haematological toxicity, no dose modification is required. If a participant experiences a Grade 3 or Grade 4 toxicity, not attributable to the disease or disease-related processes under investigation, dosing will be interrupted and/or the dose reduced (see [Table 11](#) for recommended dose modifications for AZD4573) and supportive therapy administered as required. If the toxicity resolves or reverts in line with the dose modification guidelines below and the participant was showing clinical benefit, treatment with study treatment(s) may be restarted.

If the toxicity does not resolve in line with the dose modification guidelines below, then the participant should be discontinued from the study treatment and observed until resolution of the toxicity. Maximal drug interruption allowed for AZD4573 is 21 consecutive days; in cases where more than 21 days are needed, a decision to continue, modify, or discontinue study treatment will be made on a case-by-case basis in consultation with the principal investigator and the Study Physician.

Table 11 Recommended Dose Modifications for AZD4573

Event ^a	Occurrence	Action with AZD4573	
Tumour Lysis Syndrome (TLS)			
Changes in uric acid, potassium, phosphorus, creatinine or calcium, or symptoms suggestive of TLS	Any	For any abnormal changes present before dosing, initiate supportive therapy and hold drug for up to 7 days. If not resolved, reduce by 1 dose level.	
		For events of Howard Grade 1 or 2 TLS, resume at same dose level upon resolution.	
		For first occurrence of Howard Grade 3 TLS resume at the same dose upon resolution to Grade 1.	
		For second occurrence of Howard Grade 3 TLS, after resolution to Grade 1, reduce dose by 1 dose level when re-starting AZD4573 except events that in the opinion of the investigator, in consultation with the Study Physician, are not dose limiting.	
		For subsequent occurrences of Howard Grade 3 TLS, further re-challenge and dose level to be discussed with the Study Physician.	
For events of Howard Grade 4 TLS, discontinue AZD4573.			

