Non-haematological toxicities (except liver dysfunction and TLS)			

Event ^a	Occurrence	Action with AZD4573
Grade 3 or 4 non-haematological toxicities	First occurrence	
Withhold dosing with AZD4573 until the toxicity has resolved to Grade 1, but no longer than 21 days^b.
 
Adequate supportive therapy as per Institutional guidelines should be given.
 
After resolution of Grade 3 event to Grade 1, AZD4573 therapy may be resumed at the same dose. No dose modification is required.
 
After resolution of Grade 4 event to Grade 1, reduce dose by one dose level when re-starting AZD4573.

	Second occurrence	
Withhold dosing AZD4573 up to 21 days^b.
 
Adequate supportive therapy as per Institutional guidelines should be given.
 
After resolution to Grade 1, reduce dose by one dose level when re-starting AZD4573.
 
If no resolution within 21 days discontinue AZD4573^b.

	Third occurrence	Discontinue AZD4573.
Haematological Toxicities		
Grade 3 or 4 neutropenia without fever or infection, lasting > 7 days despite growth factor support	First occurrence	
Withhold dosing AZD4573 until Grade \leq 2 or baseline level.
 
Restart at same dose level following resolution.

	Second and subsequent occurrences	
Withhold dosing AZD4573 until Grade \leq 2 or baseline level.
 
Restart with 1 dose level reduction following resolution.
 
In case of subsequent occurrences, dosing may be modified to skip weekly dose(s) (eg, 2 weeks on/1 week off or to 1 week on/1 to 2 weeks off), after discussing with the Study Physician.

Grade 3 or 4 neutropenia with infection or fever	First occurrence	
Withhold dosing AZD4573.
 
To reduce the infection risks associated with neutropenia, G-CSF may be administered with AZD4573 if clinically indicated/required as per Institutional practice.
 
Consider secondary prophylaxis with G-CSF as per ASCO/ESMO guidelines. Once the toxicity has resolved to \leq Grade 2 or to baseline level, AZD4573 therapy may be resumed at the same dose.

	Second occurrence	
Withhold dosing AZD4573.
 
Consider using G-CSF as clinically indicated/as per Institutional practice. Follow dose reduction guidelines when resuming treatment with AZD4573 after resolution.
 
Reduce dose by 1 dose level.

Event ^a	Occurrence	Action with AZD4573
	Third occurrence	Discontinue AZD4573.

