10.6.2.1.2 TLS Monitoring and Management

Please refer to [Appendix G](#) for the definition of TLS and the TLS grading criteria to be used in this study.

All participants will receive TLS prophylaxis during the intra-participant dose ramp-up and be monitored for TLS during the first 24 hours post start of infusion during the intra-participant dose ramp-up (see Sections [10.6.2.1.1](#) and [10.6.2.1.2](#)). If there are no signs of TLS at the 6 hour TLS monitoring assessment, the participant can be managed as an outpatient at the discretion of the investigator and return to the clinic the next day to complete the 24 hour TLS monitoring assessment. Participants showing signs of TLS at 6 hours after the start of infusion must remain admitted for inpatient TLS monitoring approximately every 6 hours (or more frequently if clinically indicated) until the 24 hour TLS monitoring assessment.

Where hospitalisation for longer than the mandated 24 hours is required it should be noted that if this is due to occurrence of an AE then the event must be reported as an SAE, per definition. However, if it is purely for the purposes of extended observation then this does not qualify as an SAE and does not need to be reported.

For all participants, results of safety laboratory testing (haematology and clinical chemistry at a minimum) must be available within 72 hours prior to dosing and must be reviewed by the investigator prior to each administration of AZD4573. For each TLS monitoring timepoint, a TLS Monitoring page in the eCRF is to be filled out.

In particular, the uric acid level must be < ULN prior to the start of each AZD4573 infusion.

It is strongly recommended that for all participants with elevated uric acid (hyperuricaemia) and intermediate/high risk of TLS, prophylaxis should be administered prior to AZD4573 per Section 10.6.2.1.1 and repeated as clinically indicated thereafter as per local standard.

Monitoring for TLS includes checking potassium, calcium, phosphate, uric acid, and creatinine. Fluid balance must be monitored according to institutional standards.

Any participant developing laboratory TLS must be treated promptly for electrolyte abnormalities (such as hyperkalaemia) to prevent arrhythmias/seizures and for elevated uric acid (hyperuricaemia) with rasburicase (0.20 mg/kg/d IV over 30 minutes for up to 5 days) to prevent acute renal failure and monitored closely for signs of progression to clinical TLS.

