NCI	National Cancer Institute
NK	natural killer
NKTCL	natural killer/T-cell lymphoma
OAE	other significant adverse event
ORR	overall response rate
OS	overall survival
CCI	CCI
CCI	CCI
PCR	polymerase chain reaction
PD	progressive disease
PET	positron emission tomography
PFS	progression free survival
PHL	potential Hy's Law
PK	pharmacokinetic
PK/PD	pharmacokinetic/pharmacodynamic
PR	partial response
PTCL	peripheral T-cell lymphoma
RECIST	Response Evaluation Criteria in Solid Tumors
RP2D	recommended phase II dose
r/r	relapsed/refractory
SAE	serious adverse event
SAP	Statistical Analysis Plan
SCT	stem cell transplantation
SD	stable disease
SoA	schedule of activities
SoC	standard of care
SOI	start of infusion

Abbreviation or special term	Explanation
SRC	Safety Review Committee
SUSAR	suspected unexpected serious adverse reaction
TBL	total bilirubin
TEAE	treatment emergent adverse event
TLS	tumour lysis syndrome
TPV	third-party vendor
TSH	thyroid stimulating hormone
ULN	upper limit of normal
US	United States
WOCBP	women of childbearing potential

Appendix G Cairo-Bishop Tumour Lysis Syndrome Definition and Grading Criteria (Howard Modification)

Laboratory tumour lysis syndrome (TLS) is defined as a level above or below normal, as defined below, for any 2 or more serum values of uric acid, potassium, phosphate, and calcium within 3 day before or 7 day after the initiation of anti-cancer therapy. This assessment assumes that a participant has or will receive adequate hydration and a hypouricaemic agent(s).

Cairo-Bishop Definition of Laboratory Tumour Lysis Syndrome (Howard Modification)

Element	Value
Uric Acid	$\geq 476 \mu\text{mol/L}$ (8 mg/dL)
Potassium	$\geq 6.0 \text{ mmol/L}$ (6 mg/L)
Inorganic phosphorus	$\geq 1.45 \text{ mmol/L}$ (4.5 mg/dL)
Calcium	$\leq 1.75 \text{ mmol/L}$ (7.0 mg/dL)

[Howard et al 2011](#)

Cairo-Bishop Definition of Clinical Tumour Lysis Syndrome

Clinical tumour lysis syndrome assumes the laboratory evidence of metabolic changes and significant clinical toxicity that requires clinical intervention. Clinical tumour lysis syndrome is defined as the presence of laboratory tumour lysis syndrome and any 1 or more of the below-mentioned criteria. Maximal clinical tumour lysis syndrome manifestation (renal, cardiac, neuro) defines the grade.

- (1) Creatinine $\geq 1.5 \times \text{ULN}$ (age > 12 years or age adjusted)
- (2) Cardiac arrhythmia/sudden death
- (3) Seizure

Cairo-Bishop Clinical Tumour Lysis Syndrome Grading Criteria

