Complication	Grade					
	0	1	2	3	4	5
Creatinine*,†	$\leq 1.5 \times \text{ULN}$	$1.5 \times \text{ULN}$	$1.5 - 3.0 \times \text{ULN}$	$> 3.0 - 6.0 \times \text{ULN}$	$> 6.0 \times \text{ULN}$	Death
Cardiac Arrhythmia*	None	Intervention not indicated	Nonurgent medical intervention indicated	Symptomatic and incompletely controlled	Life-threatening (eg, arrhythmia)	Death

				medically or controlled with devise (eg, defibrillator)	associated with CHF, hypotension, syncope, shock)	
Seizure*	None	None	One brief, generalised seizure; seizure(s) well controlled by anticonvulsants or infrequent focal motor seizures not interfering with ADL	Seizure in which consciousness is altered; poorly controlled seizure disorder; with breakthrough generalised seizures despite medical intervention	Seizure of any kind which are prolonged, repetitive or difficult to control (eg, status epilepticus, intractable epilepsy)	Death

ADL = activities of daily living; CHF = congestive heart failure; CTLS = clinical tumour lysis syndrome; LTLS = laboratory tumour lysis syndrome; ULN = upper limit of normal

Clinical tumour lysis syndrome (CTLS) requires one or more clinical manifestations along with criteria for LTLS. Maximal CTLS manifestation (renal, cardiac, neuro) defines the grade.

*Not directly or probably attributable to therapeutic agent (eg, rise in creatinine after amphotericin administration).

†If no institutional ULN is specified, age/sex ULN creatinine may be defined as 105.6 µmol/L for female participants \geq 16 years of age and 114.4 µmol/L for male participants \geq 16 years of age.

Modified from [Cairo and Bishop 2004](#).

Appendix H Changes Related to Mitigation of Study Disruptions Due to Cases of Civil Crisis, Natural Disaster, or Public Health Crisis

Note: Changes below should be implemented only during study disruptions due to any of or a combination of civil crisis, natural disaster, or public health crisis (eg, during quarantines and resulting site closures, regional travel restrictions and considerations if site personnel or study participants become infected with SARS-CoV-2 or similar pandemic infection) during which participants may not wish to or may be unable to visit the study site for study visits. These changes should only be implemented if allowable by local/regional guidelines and following notification from the sponsor and instructions on how to perform these procedures will be provided at the time of implementation.

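### Appendix G counts the laboratory TLS window from the start of therapy, so as written no 12 mg infusion can yield a Howard grade, in conflict with Table 11 and the SAP's per-infusion grading

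*Protocol*

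**What the plan says.** Protocol 10.6.2.1.2 refers the investigator to Appendix G "for the definition of TLS and the TLS grading criteria to be used in this study". Appendix G accepts two or more abnormal values among uric acid, potassium, phosphate and calcium as laboratory TLS only if they occur "within 3 day before or 7 day after the initiation of anti-cancer therapy". The note under its grading table adds: "Clinical tumour lysis syndrome (CTLS) requires one or more clinical manifestations along with criteria for LTLS". The grade is the worst renal, cardiac or neurological manifestation of clinical TLS.

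Other parts of the plan use that grade with no time limit:

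- Protocol 8.3.2: "TLS events will be graded according to Howard modification of the Cairo-Bishop grading system", entered on the TLS monitoring eCRF form.
- Protocol Table 11 (Section 10.6.1), TLS row, marked for any occurrence: "For events of Howard Grade 4 TLS, discontinue AZD4573". It also has separate rules for a first and a second Grade 3 event, and for subsequent occurrences "of Howard Grade 3 TLS, further re-challenge and dose level to be discussed with the Study Physician".
- Protocol 10.8.2.5: TLS chemistry before, 6 hours after and 24 hours after the start of each infusion in the ramp-up. The Schedule of Activities (Table 9) marks TLS monitoring in the column for Cycle 1, Weeks 1 to 5.
- SAP 5.6.9.1 computes the highest Cairo-Bishop grade for each infusion and participant. SAP 5.6.9.2 summarises time to TLS onset after the first dose and, separately, after later doses.

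Neither document says that initiation of therapy means each infusion.

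**The concern.** TLS is an important identified risk of AZD4573, and the dose rises from 6 mg to 9 mg to 12 mg over the first three weeks. A window that opens once, at the first dose, has closed before the target dose is given. The definitions are nested (laboratory TLS, then clinical TLS, then Howard grade), so a time limit on the first carries through to the last. In Table 11's TLS row, the only instruction that does not depend on a Howard grade is the hold for abnormal values present before dosing, followed by a one-level reduction if they do not resolve. The mandatory discontinuation depends entirely on Howard Grade 4. What is at stake is whether a site following the appendix to the letter has the grade that this rule needs after a 12 mg infusion.

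**Working it through.** **Inputs**

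- Window: 7 days after initiation (Appendix G). Module 1 is monotherapy, so initiation is taken as the first AZD4573 dose, Day 1. The SAP has no Day 0 (SAP 4.1.3.1).
- Doses: 6 mg in Week 1, 9 mg in Week 2, 12 mg in Weeks 3 to 5 (Protocol 10.4.1). Nominal days are 1, 8, 15, 22 and 29.
- Visit window: ±2 days (Table 9).

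**Window end.** Day 1 + 7 days = Day 8. If Day 1 is itself counted as the first of the seven days, the end is Day 7.

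**Position of each Cycle 1 infusion**

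| Infusion | Nominal day | Days after initiation | 24-hour sample, days after initiation | Against a 7-day limit |
|---|---|---|---|---|
| 6 mg | 1 | 0 | 1 | both inside |
| 9 mg | 8 | 7 | 8 | infusion on the last day, sample outside |
| 12 mg, first | 15 | 14 | 15 | outside |
| 12 mg, second | 22 | 21 | 22 | outside |
| 12 mg, third | 29 | 28 | 29 | outside |

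**Effect of the visit window**

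- 9 mg: 7 ± 2 = 5 to 9 days after initiation. Two days early, the 24-hour sample (5 + 1 = 6 days) is inside. Two days late, the infusion itself is outside. With the Day 7 end, even the on-schedule infusion is outside.
- First 12 mg, two days early against the nominal schedule: 14 − 2 = 12 days, which is 12 − 7 = 5 days past the limit.
- First 12 mg, if each dose is given two days early relative to the one before: 5 + 5 = 10 days, which is 10 − 7 = 3 days past the limit.

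No permitted timing brings a 12 mg infusion inside the window.

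**Following the chain.** After a 12 mg infusion, laboratory TLS is not met because of the date. Clinical TLS is then not met, there is no Howard grade, and the Grade 3 and Grade 4 instructions in Table 11's TLS row have no input.

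**Against the other provisions.** Table 11 has instructions for second and later Grade 3 events after dosing resumes. The drug is weekly, so after an event following the first dose, re-challenge comes at about Day 8 at the earliest nominal date, where the window closes. A third event could hardly ever qualify. The SAP's onset summary for later doses would likewise be confined to the 9 mg dose at most. These provisions make sense only if each infusion has its own window.

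**With a per-infusion window.** The 7 days after each infusion run from Day 8 to 15 (9 mg), then Day 15 to 22, 22 to 29 and 29 to 36 (12 mg). Every 6-hour and 24-hour sample is covered.

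**The case against.** The strongest reply is that the gap exists only if Appendix G is read alone. Table 11's TLS row covers any occurrence and provides for repeat events, eCRF grading has no time limit, ramp-up monitoring is per infusion, and the SAP grades per infusion. A sensible investigator would grade a 12 mg event. This stands as evidence of intent, and it limits the point to an inconsistency. It does not say which text governs, and Section 10.6.2.1.2 names Appendix G as the definition.

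A reader might infer three stronger things that the documents do not support.

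- **That the Grade 4 stopping rule is disabled.** The provisions above show that it is meant to apply at later infusions. Other safeguards do not need a Howard grade: CTCAE grading and special-interest reporting (8.3.2, 8.3.6), the CTCAE-based recruitment pause (7.1.1), discussion with the Study Physician before dosing resumes (6.6), discontinuation for an adverse event (7.1), hospital stay for suspected TLS (10.6.2.1.2) and the restart criteria (10.6.3).
- **That a Grade 4 event after 12 mg moves to Table 11's general non-haematological row,** where the first-occurrence instruction is "After resolution of Grade 4 event to Grade 1, reduce dose by one dose level when re-starting AZD4573". That row's heading excludes TLS, and nothing directs an investigator to treat a tumour lysis event as something else because of its date.
- **That Howard grades will differ between sites.** The eCRF form and its completion instructions are not in the documents, so this is possible but not shown.

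**Conclusion.** Wrong as written, and it should be corrected. Appendix G's single window excludes all 12 mg infusions and the 24-hour sample after an on-schedule 9 mg infusion; only the 6 mg infusion is clearly inside. It therefore conflicts with Table 11, the monitoring schedule and SAP 5.6.9. The practical exposure is narrow: a site that applies the appendix literally has no Howard grade on which to base mandatory discontinuation for Grade 4 TLS, and must rely on the other safeguards. The conclusion assumes that initiation means the first AZD4573 dose, which is the plain reading and is not redefined anywhere. SAP 5.6.9 applies no window of its own, so its outputs could be affected only through the grades that investigators enter. No efficacy analysis or sample size changes.

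**What to change.** In Appendix G, replace the time limit with: *within 3 days before the first dose or within 7 days after the start of any AZD4573 infusion*. This brings the definition into line with Table 11, the per-infusion monitoring and the SAP. SAP 5.6.9.1 already counts TLS per infusion and needs at most a cross-reference to the revised appendix. The cost is one phrase in a protocol amendment, with no new samples, visits or analyses.
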